3.1.1 Contraception Education

The risks to a fetus or to a nursing child from apremilast are not known at this time. Results of the animal and in vitro studies can be found in the IB.

All females of childbearing potential (FCBP) must use one of the approved contraceptive options as described in section 4.1.1 while on investigational product (IP) and for at least 28 days after administration of the last dose of the IP.

When a female subject of childbearing potential's contraceptive measures or ability to become pregnant changes at the time of study entry or at any time during the study, the Investigator will educate the subject regarding options and correct and consistent use of effective contraceptive methods in order to successfully prevent pregnancy.

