4.1.1 Contraception Requirements

Females of childbearing potential^a (FCBP) must have a negative pregnancy test at screening. While on investigational product and for at least 28 days after taking the last dose of investigational product, FCBP who engage in activity in which conception is possible must use one of the approved contraceptive options described below:

Option 1 - Any one of the following highly effective methods: hormonal contraception (oral, injection, implant, transdermal patch, vaginal ring); intrauterine device (IUD); tubal ligation; or partner's vasectomy;

OR

Option 2 - Male or female condom (latex condom or nonlatex condom NOT made out of natural [animal] membrane [for example, polyurethane]; PLUS one additional barrier method: (a) diaphragm with spermicide; (b) cervical cap with spermicide; or (c) contraceptive sponge with spermicide.

^a A female of childbearing potential is a sexually mature female who has not undergone a hysterectomy or bilateral oophorectomy or has not been postmenopausal for at least 24 consecutive months.

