4.2 Exclusion Criteria

6/21/2017

1. Prior use of apremilast.
2. Use of any investigational drug within 4 weeks prior to randomization, or 5 pharmacokinetic/pharmacodynamic half-lives, if known (whichever is longer).
3. Having received concomitant immune modulating therapy 12 weeks prior to enrollment, systemic steroids 6 weeks prior to enrollment or topical steroids within 4 weeks prior to enrollment.
4. Pregnant women or breast-feeding mothers.
5. Systemic or opportunistic fungal infection.
6. Known active current or history of recurrent bacterial, viral, fungal, mycobacterial or other infections (tuberculosis and atypical mycobacterial disease, hepatitis B and C and herpes zoster, histoplasmosis, coccidiomycosis) or any major episode of infection requiring hospitalization or treatment with IV or oral antibiotics within 4 weeks of the screening phase.
7. History of positive test for, or any clinical suspicion of, human immunodeficiency virus (HIV), or congenital or acquired immunodeficiency.
8. History of depression.
9. Malignancy or history of malignancy, except for:
 - a - treated (ie, cured) basal cell or squamous cell in situ skin carcinomas;
 - b - treated (ie, cured) cervical intraepithelial neoplasia (CIN) or carcinoma in situ of cervix with no evidence of recurrence within the previous 5 years.
10. Other than disease under study, any clinically significant (as determined by the Investigator) cardiac, endocrinologic, pulmonary, neurologic, psychiatric, hepatic, renal, hematologic, immunologic disease, or other major disease that is currently uncontrolled.
11. Any condition, including the presence of laboratory abnormalities, which would place the subject at unacceptable risk if he/she were to participate in the study.
12. Prior history of suicide attempt at any time in the subject's life time prior to screening or randomization, or major psychiatric illness requiring hospitalization within the last 3 years.
13. Active substance abuse or a history of substance abuse within 6 months prior to screening.
14. Presence of any of the following vitamin deficiencies - B1, B2, B6, B12, vitamin C, zinc, folate, iron.
15. Celiac disease.
16. Inflammatory Bowel Disease.
17. Genital aphthous ulcers.
18. Behçet's disease.
19. History of positive patch test for allergic contact stomatitis.
20. Positive anti-endomysial or anti-gliadin antibodies.
21. A diagnosis of uveitis (current or previous).
22. Erythema nodosum-like lesions (current or previous).

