5.4 Prior and Concomitant Therapy

Subjects will be allowed the following concomitant therapies to control flares: Tylenol, lidocaine 2% topical mouth wash and lidocaine 2% plus diphenhydramine plus Maalox topical mouth wash.

No topical and systemic therapies for RAS may be used 3 months prior to study enrollment.

6 Study Procedures

- a. The screening phase will consist of: obtaining informed consent, demographic information, medical history, inclusion and exclusion criteria, prior and concomitant medication use, adverse events; collecting vital signs and weight; performing complete physical examination, hematology, serum chemistry (vitamins B1, B6, B12, C, iron, folate, zinc, TTG, ANA), urinalysis, pregnancy testing, contraception education. Patients will also be assessed in regards to number of oral ulcers and pain visual analog scale for oral ulcers. A diary will be provided to the patient for keeping record of number and pain intensity of oral ulcers throughout the study.
- b. At baseline (week 0) all patients will undergo a complete medical history and limited physical examination, suitability assessment (inclusion and exclusion criteria), and safety assessments (adverse events, vital signs, weight, contraception education). Patients will also be assessed in relation to number of oral ulcers, pain visual analog scale for oral ulcers, physician's global assessment of oral lesions and Chronic Oral Mucosal Disease Questionnaire – COMDQ) and the investigational product will be dispensed.
- c. At week 2 all patients will undergo safety assessments (adverse events, vital signs, weight, and contraception education), efficacy assessments (number of oral ulcers, pain visual analog scale for oral ulcers, physician's global assessment of oral lesions) and investigational product accountability.
- d. At week 4 all patients will undergo safety assessments (adverse events, vital signs, weight, and contraception education), efficacy assessments (number of oral ulcers, pain visual analog scale for oral ulcers, physician's global assessment of oral lesions) and investigational product accountability. The investigational product will be dispensed.

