- e. At week 8 all patients will undergo safety assessments (adverse events, vital signs, limited physical examination, weight, contraception education, and optional lab work per Investigator's discretion, including hematology and serum chemistry), efficacy assessments (number of oral ulcers, pain visual analog scale for oral ulcers, physician's global assessment of oral lesions and Chronic Oral Mucosal Disease Questionnaire – COMDQ) and investigational product accountability. The investigational product will be dispensed.
- f. At week 12 all patients will undergo safety assessments (adverse events, vital signs, weight, and contraception education) and efficacy assessments (number of oral ulcers, pain visual analog scale for oral ulcers and physician's global assessment of oral lesions) and investigational product accountability. The investigational product will be dispensed.
- g. At week 16 all patients will undergo safety assessments (adverse events, vital signs, weight, complete physical examination, contraception education and optional lab work per Investigator's discretion, including pregnancy testing, hematology and serum chemistry), efficacy assessments (number of oral ulcers, pain visual analog scale for oral ulcers, physician's global assessment of oral lesions and Chronic Oral Mucosal Disease Questionnaire – COMDQ) and investigational product accountability.
- h. At week 24 patients will undergo safety assessments (vital signs, weight, and complete physical examination) and efficacy assessments (number of oral ulcers, pain visual analog scale for oral ulcers, physician's global assessment for oral lesions and Chronic Oral Mucosal Disease Questionnaire - COMDK).

6/21/2017

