6.1 Apremilast table of events**Schedule of Events**

Procedure	Screening phase	Baseline (Week 0)	Week 2	Week 4	Week 8	Week 12	Week 16	Week 24
Informed Consent	X							
Demography	X							
Medical History	X	X						
Inclusion/Exclusion Criteria	X	X						
Safety Assessments								
Adverse Events	X	X	X	X	X	X	X	
Vital Signs	X	X	X	X	X	X	X	X
Complete Physical Examination	X						X	X
Limited Physical Examination	X	X			X			
Weight	X	X	X	X	X	X	X	X
Hematology	X				X*		X*	
Serum Chemistry	X				X*		X*	
Urinalysis	X							
Pregnancy test	X						X*	
Contraception Education	X	X	X	X	X	X	X	
Efficacy Assessments								
Number of Oral Ulcers	X	X	X	X	X	X	X	X
Pain VAS for oral ulcers	X	X	X	X	X	X	X	X
Physician's Global Assessment of Oral Lesions	X	X	X	X	X	X	X	X
Chronic Oral Mucosal Disease Questionnaire – COMDQ	X	X			X		X	X
Investigational Product								
Dispense IP		X		X	X	X		
IP Accountability	X		X	X	X	X	X	

* lab work, including pregnancy testing, is optional per Investigator's discretion.

Statistical Plan

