7.3.1 Pregnancies

Pregnancies and suspected pregnancies (including a positive pregnancy test regardless of age or disease state) of a female subject or the female partner of a male subject occurring while the subject is on study drug, or within 30 days of the subject's last dose of study drug, are considered immediately reportable events. Study drug is to be discontinued immediately and the subject instructed to return any unused portion of the study drug to the investigator(s). The pregnancy, suspected pregnancy, or positive pregnancy test must be reported to Celgene Safety immediately facsimile using the Pregnancy Report form provided by Celgene.

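### The only required pregnancy test is at screening, so during 16 weeks of dosing the immediate stop on pregnancy rests on self-report, clinical suspicion or discretionary testing

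*Combined protocol and SAP*

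**What the plan says.** **The stop.** Section 7.3.1 treats a pregnancy, a suspected pregnancy or a positive test while on drug as immediately reportable, and adds: "Study drug is to be discontinued immediately and the subject instructed to return any unused portion of the study drug".

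**The required test.** Under section 4.1.1, females of childbearing potential "must have a negative pregnancy test at screening". No other section makes a test mandatory.

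**Baseline.** Exclusion 4 in section 4.2 reads "Pregnant women or breast-feeding mothers", and section 6 item b repeats the eligibility check at week 0. That visit lists "suitability assessment (inclusion and exclusion criteria), and safety assessments (adverse events, vital signs, weight, contraception education", but no pregnancy test. No maximum interval between screening and baseline is given.

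**On treatment.** The Schedule of Events (6.1) dispenses drug at weeks 0, 4, 8 and 12, and its pregnancy-test row is empty at all four. The optional week-8 lab work in section 6 item e is described as at the investigator's "discretion, including hematology and serum chemistry". At week 16, item g widens this to "discretion, including pregnancy testing, hematology and serum chemistry". The schedule footnote agrees: "lab work, including pregnancy testing, is optional".

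**Other controls.** Section 4.1.1 requires contraception on drug and for at least 28 days afterwards. Contraception education is scheduled at every visit to week 16. Section 3.1.1 requires re-education if a subject's contraception or ability to conceive changes. Section 7.2 requires adverse-event questioning at each contact.

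**The concern.** The plan regards exposure in pregnancy as serious enough for an immediate stop and an immediate report, and section 3.1.1 gives the reason: "The risks to a fetus or to a nursing child from apremilast are not known at this time". Yet no required procedure between screening and the end of dosing would find a pregnancy that neither the subject nor the investigator suspects.

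Two situations follow. A subject who conceives between screening and baseline can pass the repeated eligibility check and take a first dose although exclusion 4 applies to her. A subject who conceives on treatment can be given further drug at each later dispensing visit. What is at stake is avoidable fetal exposure to a drug of unstated fetal risk. No efficacy estimate is affected.

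**Working it through.** The check is a count from the schedule and some simple arithmetic.

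**Inputs**
- Dosing period: 16 weeks (Study Summary). Section 5.3 gives its parts: 1 week of titration plus 15 weeks at full dose.
- Visits from first dose to end of dosing: weeks 0, 2, 4, 8, 12 and 16 (6.1).
- Dispensing visits: weeks 0, 4, 8 and 12 (6.1).
- Pregnancy tests listed: screening (required) and week 16 (optional) (4.1.1, section 6 item g, 6.1).
- Subjects: 15 (6.2).

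**Dosing period.** 1 + 15 = 16 weeks, which reproduces the stated duration. 16 × 7 = 112 days.

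**Required tests after screening, during dosing.** 0 of 6 visits; 0 of 4 dispensing visits.

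**Dosing that a positive test at week w could still prevent.** (16 − w) × 7 days:

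| Week of test | Days of dosing left | Test in the plan |
|---|---|---|
| 0 | 112 | none listed |
| 4 | 84 | none listed |
| 8 | 56 | none listed |
| 12 | 28 | none listed |
| 16 | 0 | optional |

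The only later test in the plan sits in the row where no dosing is left to prevent. It can identify an exposed pregnancy for reporting, but it cannot shorten the exposure.

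**Age of the screening test.** At first dose its age equals the screening-to-baseline interval, which is not stated. At the end of dosing its age is 112 days plus that interval.

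**What added tests would do.** The gap is the longest stretch between required tests during dosing. Test counts assume that all 15 subjects are females of childbearing potential; 15 tests are already listed as optional at week 16.

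| Required at weeks | Longest gap | Tests at most | New tests at most |
|---|---|---|---|
| none (current plan) | 112 days | – | – |
| 0, 8, 16 | 8 × 7 = 56 days | 3 × 15 = 45 | 45 − 15 = 30 |
| 0, 4, 8, 12, 16 | 4 × 7 = 28 days | 5 × 15 = 75 | 75 − 15 = 60 |

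**The case against.** The best defence is that the plan chose a control other than testing, and that the control works.

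- **The stop does not need a test.** A reported or suspected pregnancy triggers section 7.3.1 by itself. This stands. A reader might infer that the rule contradicts the schedule or cannot operate; the documents do not support that.
- **Other controls narrow the gap.** Contraception is mandatory, education is repeated, changes in contraception prompt re-education, adverse events are asked about at each contact, and there is a limited physical examination at week 8. This also stands, but these measures prevent a pregnancy or depend on someone suspecting one. None reliably finds an unrecognised one.
- **The investigator may test at any time.** Nothing forbids it. The week-8 wording is not an exhaustive list, and the schedule footnote also covers the starred week-8 laboratory entries. A reader might infer that testing before week 16 is excluded; it is only not required.
- **112 days is a ceiling.** It needs a pregnancy present at first dose that stays unreported and unsuspected to week 16. The documents give no probability for this and no number of females of childbearing potential, so it must not be read as an expected exposure.
- **Other sources may fill the gap.** Section 3.1.1 refers to the Investigator's Brochure for animal and in vitro results. The brochure, the consent form and the separate monitoring plan are not in the documents and might add a test. That limits confidence, but the protocol's own schedule makes the only later test optional.

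A reader might also extend the point to week 24, on the ground that pregnancies in the 30 days after the last dose could be missed. The documents do not support this. There is no drug left to stop, such pregnancies remain reportable under 7.3.1, and 7.1 and 7.2 carry adverse-event monitoring and questioning through follow-up. For the same reason week 24 is left out of the visit count.

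**Conclusion.** The point holds in a limited form. Between the screening test and the end of dosing the plan requires no pregnancy test, and the one later test listed is optional and too late to prevent any dosing. The immediate stop therefore rests on self-report, clinical suspicion or discretionary testing. Followed exactly, the plan could start drug in a subject already pregnant, or keep supplying it to one.

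The largest possible exposure is 112 days, which required contraception makes unlikely. This assumes that the schedule in 6.1 is complete and that no document outside the protocol adds a test. It is a minor subject-safety improvement and is worth making because it is cheap. It has no bearing on the efficacy analysis.

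**What to change.** In 4.1.1, section 6 and the Schedule of Events, for females of childbearing potential:

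1. Require a negative urine pregnancy test at baseline, before the first dose.
2. Require a test during treatment at existing dispensing visits: at minimum week 8, preferably weeks 4, 8 and 12.
3. Make the week-16 test mandatory, and reword item g and the footnote to match.
4. State that drug is not dispensed on a positive test, and that a missed test is done at the same visit before dispensing. Doing the missed test on the spot avoids a treatment interruption, for which sections 5.2 and 5.3 give no restart or re-titration rule.

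The cost is at most 75 urine tests, 60 of them new, for the fuller schedule, or 45 tests, 30 of them new, for weeks 0, 8 and 16. Both figures assume that all 15 subjects are of childbearing potential, so the true number will be lower if any are not. No visit is added. How often to test during treatment is a judgement for the investigator; the baseline test and at least one on-treatment test are the essential part.

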7.3.2 Sponsor-Investigator reporting: notifying the Mayo IRB

The sponsor-investigator will report to the Mayo IRB any UPIRTSOs and Non-UPIRTSOs according to the Mayo IRB Policy and Procedures.

7.4 Stopping Rules

Study enrollment and treatment procedures will be suspended in the event that a subject experiences treatment related Adverse Event while on study. The study would only be resumed after a thorough review of the incidents and any corrective and preventative actions have been put in place along with consultation between the study team and the IRB.

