1.4 Dose Rationale and Risk/Benefits

Based on the safety and efficacy of previous studies using apremilast for Behçet's disease and psoriasis, the dose of apremilast 30mg was chosen for the present study. Subjects will receive apremilast 30mg twice daily for 16 weeks. Since apremilast is known to be associated with gastrointestinal side effects and headaches, the dose will be increased gradually during the first week of treatment until the full 30mg dose is reached.

The expected benefits from apremilast use include reduction in the number and duration of oral ulcers, decreased oral ulcer pain, improved physical function and quality of life in patients with RAS. Risks associated with apremilast therapy include possible gastrointestinal side effects, headaches, upper respiratory tract infection, hypersensitivity reactions and depression.

2 Study Objectives

Primary Objective

- To evaluate the efficacy of apremilast for the treatment of RAS.

Secondary Objectives

- To evaluate the safety and tolerability of apremilast in subjects with RAS.

3 Study Design

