4.4 Early Withdrawal of Subjects

4.4.1 When and How to Withdraw Subjects

Subjects may withdraw from the study at any time for the following:

- Subject safety issues related to serious reactions such as bacterial or viral skin infection, fever, or tissue hypertrophy.
- Subject decision to withdraw from the study (withdrawal of consent)
- Subject's decision to pursue other therapeutic regimens, either surgical or non-surgical

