5.2 Treatment Regimen

Subjects will receive apremilast 30mg twice daily for 15 weeks. Since Apremilast is known to be associated with gastrointestinal side effects and headaches, the dose will be increased gradually in the first week according to the following schedule:

Day 1: 10mg in morning

Day 2: 10mg in morning and 10mg in evening

Day 3: 10mg in morning and 20mg in evening

Day 4: 20mg in morning and 20mg in evening

Day 5: 20mg in morning and 30mg in evening

Day 6 and thereafter: 30mg twice daily

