7.1 Definitions

Unanticipated Problems Involving Risk to Subjects or Others (UPIRTSO)

Any unanticipated problem or adverse event that meets the following three criteria:

- Serious: Serious problems or events that results in significant harm, (which may be physical, psychological, financial, social, economic, or legal) or increased risk for the subject or others (including individuals who are not research subjects). These include: (1) death; (2) life threatening adverse experience; (3) hospitalization - inpatient, new, or prolonged; (4) disability/incapacity - persistent or significant; (5) birth defect/anomaly; (6) breach of confidentiality and (7) other problems, events, or new information (i.e. publications, DSMB reports, interim findings, product labeling change) that in the opinion of the local investigator may adversely affect the rights, safety, or welfare of the subjects or others, or substantially compromise the research data, **AND**
- Unanticipated: (i.e., unexpected) problems or events are those that are not already described as potential risks in the protocol, consent document, not listed in the Investigator's Brochure, or not part of an underlying disease. A problem or event is "unanticipated" when it was unforeseeable at the time of its occurrence. A problem or event is "unanticipated" when it occurs at an increased frequency or at an increased severity than expected, **AND**
- Related: A problem or event is "related" if it is possibly related to the research procedures.

Adverse Event

An untoward or undesirable experience associated with the use of a medical product (i.e. drug, device, biologic) in a patient or research subject.

Serious Adverse Event

Adverse events are classified as serious or non-serious. Serious problems/events can be well defined and include;

- death
- life threatening adverse experience
- hospitalization inpatient, new, or prolonged;
- disability/incapacity
- persistent or significant birth defect/anomaly

- important medical event

Important medical events are defined as those occurrences that may not be immediately life threatening or result in death, hospitalization, or disability, but may jeopardize the subject or require medical or surgical intervention to prevent one of the other outcomes listed above.

or other events that in the opinion of the sponsor-investigator may have adversely affected the rights, safety, or welfare of the subjects or others, or substantially compromised the research data.

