All adverse events that do not meet any of the criteria for serious, should be regarded as **non-serious adverse events**.

Adverse Event Reporting Period

For this study, the study treatment follow-up period is 6 months after enrollment. The adverse event monitoring period will end at the end of the follow-up period. If an event is reported after this time it would need to be determined whether or not it is study related.

Preexisting Condition

A preexisting condition is one that is present at the start of the study. A preexisting condition should be recorded as an adverse event if the frequency, intensity, or the character of the condition worsens during the study period.

General Physical Examination Findings

At screening, any clinically significant abnormality should be recorded as a preexisting condition. At the end of the study, any new clinically significant findings/abnormalities that meet the definition of an adverse event must also be recorded and documented as an adverse event.

Post-study Adverse Event

All unresolved adverse events should be followed by the sponsor-investigator until the events are resolved, the subject is lost to follow-up, or the adverse event is otherwise explained. At the last scheduled visit, the sponsor-investigator should instruct each subject to report, to the sponsor-investigator, any subsequent event(s) that the subject, or the subject's personal physician, believes might reasonably be related to participation in this study.

Abnormal Laboratory Values

A clinical laboratory abnormality should be documented as an adverse event if it was exhibited as a severe reaction i.e. swelling, that required hospitalization or additional clinical intervention.

Hospitalization, Prolonged Hospitalization or Surgery

Any adverse event that results in hospitalization or prolonged hospitalization should be documented and reported as a serious adverse event unless specifically instructed otherwise in this protocol. Any condition responsible for surgery should be documented as an adverse event if the condition meets the criteria for an adverse event.

Neither the condition, hospitalization, prolonged hospitalization, nor surgery are reported as an adverse event in the following circumstances:

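### Section 7.4 requires study-wide suspension after any one treatment-related adverse event, so an expected mild headache meets the trigger

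*Combined protocol and SAP*

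**What the plan says.** Section 7.4 (Stopping Rules) has two sentences. The first sets the trigger and the action: "Study enrollment and treatment procedures will be suspended in the event that a subject experiences treatment related Adverse Event while on study". The second begins "The study would only be resumed after a thorough review of the incidents" and adds that any corrective and preventative measures must be in place and the study team must have consulted the IRB. The suspension is mandatory, and because the second sentence speaks of the study resuming, it applies to the whole study.

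Section 7.1 opens its definition of an adverse event with "An untoward or undesirable experience associated with the use of a medical product". It then lists the criteria for a serious event and sets up a residual non-serious class: "All adverse events that do not meet any of the criteria for serious, should be regarded as" non-serious. Section 7.4 uses the term adverse event and does not refer to either class.

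Section 1.4 introduces the gradual first-week dose increase with "Since apremilast is known to be associated with gastrointestinal side effects and headaches". Section 5.2 repeats that reason and gives the schedule: "the dose will be increased gradually in the first week according to the following schedule". The wider risk statement in 1.4 is: "Risks associated with apremilast therapy include possible gastrointestinal side effects, headaches, upper respiratory tract infection, hypersensitivity reactions and depression".

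Section 3.4 makes the type, frequency, severity and drug relationship of adverse events a safety endpoint. Section 6.3 plans to estimate the proportion of subjects with adverse reactions, with a 95% confidence interval.

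**The concern.** The protocol expects certain mild drug effects, titrates to reduce them and plans to count them. Its stopping rule then treats the first such effect as a reason to suspend enrolment and treatment procedures for everyone. If staff follow the rule, an expected mild reaction stops the study until the review and IRB consultation are done. If they carry on through such reactions, they breach a mandatory safety provision of their own protocol.

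A second gap makes the rule hard to carry out. The term for the treatment activities that stop is not defined. The schedule of events in 6.1 dispenses drug at weeks 0, 4, 8 and 12 for use at home. Nothing in 7.4 says whether a suspension stops subjects who are already dosing, or only new starts and new dispensing.

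**Working it through.** **Reading the text**

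1. *Number of events needed.* Section 7.4 requires one subject with one related event. It states no count.
2. *Kind of event.* The only qualifier in 7.4 is relatedness. Section 7.1 covers non-serious events, and 7.4 does not exclude them. The definitions in 7.1 also offer seriousness and unexpectedness as criteria (in the definition of unanticipated problems), but 7.4 uses neither.
3. *Limits elsewhere in 7.1.* A laboratory abnormality counts as an adverse event only if it appeared as a severe reaction needing hospitalization or further intervention, and a preexisting condition counts only if it worsens. These limits narrow the trigger somewhat. Neither exempts a new gastrointestinal symptom or headache.
4. *Is such an event expected?* Yes, by 1.4 and 5.2.

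A mild headache judged related to apremilast therefore meets the trigger.

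**How often the rule might be triggered**

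The plan states no event rate and no operating characteristic for the rule, so there is no figure to reproduce. The calculation below is an illustration.

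Inputs: n = 15 treated subjects (section 6.2; all receive apremilast by section 3.1). Let p be the chance that a subject has at least one related adverse event of any grade. The values of p are assumed, and subjects are taken as independent.

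P(at least one trigger) = 1 − (1 − p)^15

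| Assumed p | Calculation | P(at least one trigger) |
|---|---|---|
| 3% | 1 − 0.97^15 | 37% |
| 5% | 1 − 0.95^15 | 54% |
| 10% | 1 − 0.90^15 | 79% |
| 20% | 1 − 0.80^15 | 96% |
| 30% | 1 − 0.70^15 | 99.5% |

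The rate at which a trigger becomes more likely than not is p = 1 − 0.5^(1/15) = 0.045, about 4.5%.

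**The same calculation for a related serious event**

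Here p is the assumed per-subject chance of a related serious event:

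- p = 0.5%: 1 − 0.995^15 = 7%
- p = 1%: 1 − 0.99^15 = 14%
- p = 2%: 1 − 0.98^15 = 26%

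These three figures cover only the serious-event part of the trigger proposed below. That trigger also has a part that rests on judgment, for which no rate can be assumed, so they are a floor for the amended rule.

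All of these are chances that the rule is triggered at least once. They are not counts of suspensions and say nothing about the size of any effect on the endpoint.

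**The case against.** The strongest defence is that this is deliberate caution. The study is a small single-site pilot with descriptive analysis and no power calculation, and the IRB approves the protocol. An automatic pause with IRB consultation protects subjects, and how much caution to require is a matter of risk tolerance. The authors may also have had serious or unanticipated events in mind: 7.5 speaks of regular assessment of serious events, and the separate data and safety monitoring plan mentioned in 9.1 may set out practical handling.

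Part of this stands. The rule errs towards protection, which keeps the severity down, and the threshold is for the sponsor-investigator and IRB to settle. But if serious events were meant, a mandatory rule should say so. Section 7.5 does not limit 7.4. The monitoring plan was not available for this review, and 7.4 does not defer to it; a narrower plan would still leave the two documents to be reconciled.

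A reader might infer three stronger conclusions that the documents do not support.

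- *That the study halts at a lower bar than a single subject's withdrawal.* The safety ground in 4.4.1 is "Subject safety issues related to serious reactions such as bacterial or viral skin infection, fever, or tissue hypertrophy". But 4.4.1 lists permissive grounds for leaving, among them the subject's own decision, while 7.4 is a reversible pause. Section 3.4 also counts discontinuations for any adverse event. The two thresholds are not on one scale.
- *That a suspension is probable.* This needs a rate above about 4.5%, and the documents give none.
- *That the week 16 ulcer count would be biased.* Nothing here establishes a size or direction.

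**Conclusion.** The point holds: 7.4 is wrong as written, as an over-broad mandatory rule, with low-to-moderate severity. It is not a logical contradiction, since a study can be required to pause for events it expects. The textual finding depends on no assumed rate.

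The practical size does. A trigger somewhere among 15 subjects has a chance of 37% at an assumed rate of 3% and 99.5% at 30%, given independent subjects who are all treated. The harm is operational and a matter of compliance: either the study is interrupted for an expected mild effect, or its safety rule is not followed.

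**What to change.** Amend 7.4 so that the trigger reads, in substance:

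> A treatment-related event that meets a medical seriousness criterion in 7.1 (death, life-threatening event, hospitalization, disability, birth defect or important medical event); or any other treatment-related event, including depression or hypersensitivity, that the sponsor-investigator judges an unacceptable risk to other subjects.

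Then add:

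- Non-serious gastrointestinal effects and headache are recorded under 7.2 and managed in the affected subject without suspending the study.
- Other non-serious related events are reviewed promptly under 7.5.
- The text states whether suspension stops current home dosing, or only new starts and dispensing.
- The data and safety monitoring plan is aligned with 7.4.

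Three simpler repairs should be avoided. Exempting the whole risk list in 1.4 would exempt hypersensitivity and depression. Using the definition of unanticipated problems would bring in non-medical harms such as a confidentiality breach. Citing the full 7.1 definition of a serious event would do much the same, because it ends in a catch-all that covers subjects' rights and compromised data. For that reason the medical criteria are listed.

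The cost is a short amendment with IRB review and no added patients or visits. The downside is that non-serious related events no longer force a pause and IRB consultation. Early notice of a cluster, including non-serious depression or hypersensitivity, then relies on recording under 7.2, oversight under 7.5 and the sponsor-investigator's judgment. The IRB should confirm that it accepts this threshold.
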